Trial: Basic demographics of the participants will be summarized quantitatively in a way that characterizes the study participants but cannot be traced to individuals.

HFrEF medication dose optimizations (initiations and intensifications) at 1-month and study end will be obtained from the Epic electronic health record and summarized as a count.

Analyses of effectiveness for the primary outcome of dose optimizations will use a repeated measures mixed model. This strategy allows for partially incomplete data (e.g. missing follow-up or one of the patient/caregiver pair) and relaxes missing data assumptions to missing at random conditional on observed data. Prior to these analyses, we will contrast the participants in the arms of the study, identifying any patient/site characteristics that are unbalanced. If more than 3-5 variables are identified, we will develop a propensity score for the likelihood of being in the intervention phase as a secondary analysis. Each analysis model will include an indicator variable for the intervention phase, indicators for each of the sites and the variables identified above.

Quantitative questionnaire data will be scored and summarized according to the methods previously validated and published for each questionnaire. Significance for differences between quantitative statistics will be determined using Chi-square tests.

We will use the following measures:

- Prescribed dose optimizations: Number of initiations and dose intensifications of HFrEF medications.
- Patient Activation Measure: To measure patient activation, we use the 13-item Patient Activation Measure (PAM) developed by Hibbard et al.
- Feasibility: To evaluate feasibility, we will explore participation rates and adherence to the study protocol. Additionally, we will collect information on how the patient and providers perceived the usefulness of the materials, through qualitative interviews conducted during the pilot phase.
- Patient Assessment of Care for Chronic Conditions Survey: Patient perceptions of medical care will be assessed using the Patient Assessment of Care for Chronic Conditions Survey (PACIC) developed by Glasgow et al.
- Control Preferences Scale (preferred): We will measure the participants' preferred role in decision making using the validated Control Preferences Scale.
- Proportion of Days Covered (PDC): Prescription fills compared to the ideal, expressed as a percent of days covered.

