Sample Size: The primary outcome of dose optimizations is used to guide study size. Based on data review from a sample of ambulatory patients with HFrEF seen at University of Colorado Hospital as well as prior work characterizing ambulatory HFrEF care in Denver ([name] K23),¹³ the average number of dose adjustments over a year period is approximately 0.5 (0.6 SD); most dose adjustments occur around the time of hospitalization for decompensation. We assume at least half of patients in the intervention will involve the video and Option Grid in their clinical encounters, and that half of them will experience an average of 1 additional medication optimization. In summary, we surmise that 25% of patients randomized to EPIC-HF realizing additional medication optimization is clinically significant and possible. Assuming a Poisson distribution for the outcome as a count, with a 2-sided alpha of 0.05, a 1-year mortality rate of 15% among ambulatory HFrEF patients,⁵³ and a drop-out rate of 10%, with comparison of each intervention arm to the control, study of 255 patients should allow for reasonable power (>80%) to assess the primary endpoint as well perform hypothesis testing around secondary measures and predetermined subgroup analyses. Due to experiences from other studies of a large dropout rate with this patient population (due to death, withdrawal, and lost to follow-up from severe illness and/or lack of return to UCH medical center for care), we will allot for enrollment of 315 patients.

For the pilot trial, we will enroll no more than 60 patients and clinicians spread between North, South, and Metro/Central.

G. Summarize Knowledge to be Gained:

Pilot: By understanding how a sample of patients engage with and react to the intervention materials, the pilot study will illuminate barriers to implementation of the intervention, as well as any critical flaws with the materials.

Trial: By formally testing, on a multi-site level, the effectiveness of the intervention, we will help inform how best to support patients and providers navigate the complexities of HFrEF prescribing, and whether increased patient engagement around their medication plans leads to improved provider prescribing habits.

H. References:

1. [name] LA, Fonarow GC, Liang L, et al. Medication Initiation Burden Required to Comply With Heart Failure Guideline Recommendations and Hospital Quality Measures. *Circulation*. 2015;132(14):1347-1353.

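### The stated Poisson model gives 255 patients about 71% power at the minimum effect, or 59–60% in the worst case for losses; >80% after losses needs a different variance

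*Combined protocol and SAP*

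**What the plan says.** All the inputs are in the Sample Size paragraph of Section IV.F, except the number of arms, which is in Section IV.C.

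- **Control rate:** "the average number of dose adjustments over a year period is approximately 0.5 (0.6 SD".
- **Effect:** "We assume at least half of patients in the intervention will involve the video", and "half of them will experience an average of 1 additional medication optimization". The paragraph sums this up as a quarter of intervention patients gaining an optimization.
- **Model, error rate and losses:** "Assuming a Poisson distribution for the outcome as a count, with a 2-sided alpha of 0.05, a 1-year mortality rate of 15"%, together with 10% drop-out.
- **Conclusion:** "study of 255 patients should allow for reasonable power (>80%) to assess the primary endpoint as well perform hypothesis testing around secondary measures".
- **Enrolment:** after citing large drop-out in other studies, "we will allot for enrollment of 315 patients".
- **Comparison:** "with comparison of each intervention arm to the control", although the Randomization text in Section IV.C has one intervention arm and one control arm.
- **Analysis:** elsewhere in Section IV.F, the primary outcome "will use a repeated measures mixed model". The power statement makes no use of that model.

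The paragraph does not give the formula, the variance used, the allocation ratio, or whether 255 counts patients before or after losses.

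**The concern.** A Poisson count has variance equal to its mean. A control mean of 0.5 therefore implies a variance of 0.50 (SD 0.71), while the quoted SD of 0.6 implies 0.36. The same paragraph offers both, and the power depends heavily on which was used. Under Poisson, the stated >80% is not reached with 255 patients at the planned effect.

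This paragraph is the only justification of the trial's size. If the primary result is null, a reader will want to know how likely the trial was to detect the minimum effect. At 315 enrolled, with nothing from lost patients, the answer runs from about 68% to about 90% depending on an assumption that the text does not state.

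**Working it through.** **Inputs.** Control mean 0.5. Minimum effect 0.5 × 0.5 × 1 = 0.25, so 0.50 versus 0.75. Two-sided 0.05. Losses of 15% and 10%: the retained fraction is 0.85 × 0.90 = 0.765, or 0.75 if the two are added. Allocation of 1:1 is my assumption.

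**Formula.** For an unadjusted comparison with n patients per arm and arm variances v0 and v1: power = Φ(0.25 / √((v0 + v1)/n) − 1.96).

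**n per arm.**
- 255 enrolled: 127.5 with no loss; 97.5 (× 0.765) or 95.6 (× 0.75) if lost patients contribute nothing.
- 315 enrolled: 157.5 with no loss; 120.5 or 118.1 if lost patients contribute nothing.

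**Attempt to reproduce >80% at 255.** With the stated Poisson model, v0 + v1 = 0.50 + 0.75 = 1.25.
- All evaluable: 0.25/√(1.25/127.5) = 2.525, and Φ(2.525 − 1.96) = 71%.
- Lost patients contribute nothing: 0.25/√(1.25/97.5) = 2.208 gives 60%; with n = 95.6, 2.187 gives 59%.

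The choice of test does not explain the gap. With all 255 evaluable, score, log rate ratio and square-root versions give 71–72%, simulated Wald and likelihood-ratio tests agree, and an exact conditional test gives 69%.

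**Other variance assumptions:**

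| Variance assumption | v0 + v1 | 255, no loss | 255, lost give nothing | 315, no loss | 315, lost give nothing |
|---|---|---|---|---|---|
| Poisson, each arm's own | 0.50 + 0.75 = 1.25 | 71% | 59–60% | 80% | 68–69% |
| Poisson control variance in both arms | 0.50 + 0.50 = 1.00 | 81% | 69% | 88% | 78% |
| SD 0.6, plus fixed gain of one in 25% | 0.36 + 0.5475 = 0.9075 | 84% | 73–74% | 91% | 81–82% |
| SD 0.6 in both arms | 0.36 + 0.36 = 0.72 | 91% | 82–83% | 96% | 89–90% |

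In the third row, a gain of exactly one in a random quarter of patients adds 0.25 × 0.75 = 0.1875 to the intervention variance.

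To have 80% power at 255 the variance sum must not exceed n × (0.25/2.802)². That is 1.015 with no loss, and 0.76–0.78 if lost patients contribute nothing. In the table, only SD 0.6 in both arms meets the second limit.

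**Partial follow-up under Poisson.** Suppose the 25% lost contribute half their follow-up (an assumption). Poisson information scales with person-time, so n is multiplied by 0.875. Power is then 66% at 255 (n = 111.6) and 75% at 315 (n = 137.8).

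**Sensitivity to the assumed inputs, Poisson, 255 evaluable.**
- The variance-optimal split (about 55% to intervention) gives (√0.50 + √0.75)² = 2.475, and 0.25/√(2.475/255) = 2.538, which is 72%.
- A control mean of 0.45 gives 0.25/√(1.15/127.5) = 2.632, which is 75%.

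**Uptake needed for 80% under Poisson** (difference = 0.5 × uptake): 56% (difference 0.281) with 255 evaluable; 66% (0.330) with 255 enrolled and 25% giving nothing; 54–59% (0.269–0.293) at 315 with 25% lost, for half or no follow-up.

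**What 255 might mean.** Losses are listed among the inputs to 255, which suggests enrolled patients. Raising the number to 315 because of drop-out suggests evaluable ones. On the second reading, the stated losses leave 315 × 0.75 = 236 to 315 × 0.765 = 241, not 255.

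**The case against.** **The paragraph's own figures do reproduce >80%.** This is the strongest reply and it is partly right. A difference of 0.25, SD 0.6 in both arms and both losses give 82–83% at 255. A reader might infer from the Poisson result that the claim is impossible or that the trial is underpowered; the documents support neither. But this route sets aside the model that the paragraph names. It also requires that an intervention from which a quarter of patients gain adds no spread. That it was the route used is a guess.

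**The 59–60% is a worst case.** This stands. Prescribing data come from the health record at 1 month and at study end, and the analysis text allows for incomplete data, so many lost patients may contribute something. The favourable figure, 71%, is still below 80%.

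**An SD of 0.6 does not disprove Poisson.** This also stands. A reader might take the two as contradictory, and rounding alone does not close the gap: for means of 0.45–0.55 and SDs of 0.55–0.65, variance/mean is 0.55–0.94. But the 0.6 comes from a sample of unstated size. In simulated Poisson samples with a mean in that range, the SD fell below 0.65 in about 33%, 30% and 16% of samples of 30, 50 and 100 patients (sizes assumed). The point is only that 0.36 and 0.50 give different power and the text does not choose.

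**The effect is a floor.** True, and higher uptake would raise power. The plan gives no figure above one half.

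**The planned model is adjusted.** A reader might expect covariates to recover the shortfall. Under Poisson they do not: if counts are Poisson given the covariates, the residual variance stays at the mean. In simulations at 255 (0.5 versus 0.75, log-rate SD of the covariate from 0 to 0.7, 1,500 runs each), adjusted Poisson power stayed at 70–72%.

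**Conclusion.** The concern holds as a mismatch between the stated model and the stated power. At the minimum effect, Poisson variance gives 71% with all 255 evaluable and 59–60% if lost patients contribute nothing, against the claimed >80%. After losses, the claim is recovered only with SD 0.6 in both arms, and falls to 73–74% once a fixed gain in a quarter of intervention patients is allowed for.

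This rests on a difference of exactly 0.25, 1:1 allocation and an unadjusted comparison. It does not show that the trial is too small. At the planned 315, the minimum effect has 68–80% power under Poisson, depending on losses, and 81–90% with SD 0.6 and nothing from lost patients. Nor does the phrase about each intervention arm show a third arm; with two arms defined in Section IV.C, it is a wording slip. The paragraph should be corrected because the trial's size rests on it, and the correction is cheap.

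**What to change.** Leave enrolment at 315 and rewrite the Sample Size paragraph.

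1. Base the power statement on one variance assumption and give its source.
2. Say whether 255 is enrolled or evaluable, state the allocation ratio, and say how patients lost early contribute.
3. Restate power at 315, noting that 0.25 is a minimum difference and that higher uptake would raise power.
   - *If Poisson is kept:* with 315 enrolled 1:1 and 0.5 versus 0.75 optimizations per year, a two-sided 0.05 comparison has about 80% power with no losses, 75% if the 25% lost contribute half their follow-up, and 68–69% if they contribute nothing.
   - *If SD 0.6 is kept:* with lost patients contributing nothing, power is about 89–90% with SD 0.6 in both arms, or 81–82% with SD 0.6 in controls and a fixed gain of one in 25% of intervention patients.
4. As wording only, refer to the intervention arm in the singular.

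The cost is one rewritten paragraph, with no added patients and no change of design. The downside is that the stated power becomes less favourable if Poisson is kept: below 80% at the minimum effect once the stated losses are counted.
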